| | | |
|---------------------------------------------------------------------------------|------------------------------------------------------------------------|-----------------------|
|  | Treatment with the Evoke System for Facial and Submental Laxity | |
| | Protocol No: DO609886A SIRB ID: | Rev. Date: 29 Oct. 20 |

STUDY NAME: TREATMENT WITH THE EVOKE SYSTEM FOR FACIAL AND
SUBMENTAL LAXITY

DOCUMENT DATE: October 29, 2020

IDENTIFIERS: NCT04719013

PROTOCOL ID: DO609886A

| | | |
|--------------------------------------------------------------------------------------------------------|------------------------------------------------------------------------|-----------------------|
|  I N M O D E | Treatment with the Evoke System for Facial and Submental Laxity | |
| | Protocol No: DO609886A SIRB ID: | Rev. Date: 29 Oct. 20 |

Study Name: **Treatment with the Evoke System for Facial and Submental Laxity**

Protocol No.:

Revision No.: 1

Sponsor: **InMode Ltd.**
[name]
[name]
[name]
[name]
[contact]
[contact]

| | | |
|--------------------------------------------------------------------------------------------------------|-----------------------------------------------------------------|-----------------------|
|  I N M O D E | Treatment with the Evoke System for Facial and Submental Laxity | |
| | Protocol No: DO609886A SIRB ID: | Rev. Date: 29 Oct. 20 |

1. Protocol Synopsis

| | |
|-------------------------------------------|---------------------------------------------------------------------------------------------------------------------------------------------------------------------------------------------------------------------------------------------------------------------------------------------------------------------------------------------------------------------------------------------------------------------------------------------|
| Study Title | Treatment with the Evoke System for Facial and Submental Laxity |
| Protocol No | DO609886A |
| Sponsor | InMode Ltd. |
| Investigational Product | Evoke (K191855) |
| Study Design | Prospective, open label clinical study. |
| Study Sites | #1-, #2-, #3-, #4-, #5- |
| Patient Population and Sample Size | Subjects aged 35-75, healthy adults with visible signs of aging, seeking skin laxity treatments. Approximately 15 subjects will be enrolled per site Treatment areas include face, under chin (submental) |
| Study Duration | Study duration for each subject is approximately 10 months (including screening, three treatments once in 2 weeks and 3 follow-up visits at 1m (except site #3), 3 months and 6 months post last treatment. Overall study duration will be approximately 14 months, depending on the subject recruitment rate. |
| Study Objectives | The aim of the study is to evaluate the efficacy, patient comfort, and patient satisfaction after Evoke treatment for face and submental area |
| Primary Objective | 
 1. Evaluate improvement in skin appearance comparing pre and at 1 month (except site #3), 3 months and 6 months post last treatment photographs (as assessed by blinded investigators) 2. Evaluate Improvement in skin appearance using 3D Photographic analysis at 1month (except site #3), 3 months and 6 months follow up visits and compared to the baseline. |
| Secondary Objectives | 
 1. Evaluate Investigator assessment of the skin appearance improvement comparing pre and post treatment using 0 - 4 -points Likert scale at 1month (except site #3), 3 months and 6 months follow up visits. 2. Evaluate Subject assessment of improvement and satisfaction using 0 - 4 -points Likert scale at 1month (except site #3), 3 months and 6 months follow up visits. |

| | | |
|--------------------------------------------------------------------------------------------------------|------------------------------------------------------------------------|-----------------------|
|  I N M O D E | Treatment with the Evoke System for Facial and Submental Laxity | |
| | Protocol No: DO609886A SIRB ID: | Rev. Date: 29 Oct. 20 |

| | |
|---------------------------|----------------------------------------------------------------------------------------------------------------------------------------------------------------------------------------------------------------------------------------------------------------------------------------------------------------------------------------------------------------------------------------------------------------------------------------------------------------------------------------------------------------------------------------------------------------------------------------------------------------------------------------------------------------------------------------------------------------------------------------------------------------------------------------------------------------------------------------------------------------------------------------------------------------------------------------------------------------------------------------------------------------------------------------------------------------------------------------------------------------------------------------------------------------------------------------------------------------------------------------------------------------------------------------------------------------------------------------------------------------------------------------------------------------------------------------------------------------------------------------------------------------------------------------------------------------------------------------------------------------------------------------------------------------------------------------------------------------------------------------------------------------------------------------------------------------------------------------------------------------------------------------------------------------------------------------------------------------------------------------------------------------------------------------------------------------------------------------------|
| | 
 3. Optional: Evaluate histological changes to treatment area skin taken at 3M FU versus baseline. (except site #3) |
| Efficacy Endpoints | 
 1. Improvement in skin appearance comparing pre and at 1 month (except site #3), 3 months and 6 months post last treatment photographs (as assessed by blinded investigators): 
 • Success is defined by correct identification of the pre and post treatment photos of patients completed the treatment at 1 month (except site #3), 3 months and 6 months post treatment. • At least 2 out of 3 blinded evaluators should agree on the assessment. 2. 3D Photographic analysis will be conducted at 1 month (except site #3), 3 months and 6 months follow up visits and compared to the baseline. 3. Investigator assessment of the skin appearance improvement comparing pre and post treatment using 0 - 4 -points Likert scale at 1 month (except site #3), 3 months and 6 months follow up visits: 
 • 4 = Significantly marked improvement; 3 = Marked improvement; 2 = Moderate improvement; 1 = Slight improvement; 0 = No difference 4. Improvement assessment will be performed independently by the subject himself 4 points Likert scale questionnaire (Global Aesthetic Improvement Scale), as follows: 
 • 4 = Significantly marked improvement; 3 = Marked improvement; 2 = Moderate improvement; 1 = Slight improvement; 0 = No difference. 5. Subject assessment of satisfaction will be filled out by subjects using a 5-points Likert scale, as follows: 
 • +2 = Very satisfied; +1 = Satisfied; 0 = Indifferent; -1 = Disappointed; -2 = Very disappointed. 6. Optional: Positive changes in histologic evaluation: up to 5 subjects will undergo biopsies of the treated area for histology at baseline and at 3M follow-up visit. Histological sections will be stained using elastin, H&E and other collagen specific stains. (except site #3) |
| Safety Endpoint | 
 • Observation, assessment and recording of adverse events. • Discomfort Level assessment - subject will be asked to rate discomfort during the procedure. Discomfort will be assessed based on the Numerical Scale Response (NSR). The subject will be presented a scale and asked to make a mark along the scale. The subject will be asked to rate discomfort from 0 to 10, with 0 equaling no discomfort and 10 equaling the worst possible discomfort. A number is obtained by measuring up to the point the subject has indicated. (Appendix 3 – Discomfort Assessment) • Evaluations will be done immediately after treatments and at all follow-up visit. The frequency, severity and causality of all adverse events will be recorded. |

| | | |
|---------------------------------------------------------------------------------|------------------------------------------------------------------------|-----------------------|
|  | Treatment with the Evoke System for Facial and Submental Laxity | |
| | Protocol No: DO609886A SIRB ID: | Rev. Date: 29 Oct. 20 |

Statement of Compliance

This study will be conducted in accordance with the Code of Federal Regulations on the Protection of Human Subjects (45 CFR Part 46), any other applicable US government research regulations, and institutional research policies and procedures. The Principal Investigator will assure that no deviation from, or changes to the protocol will take place without prior agreement from the sponsor and documented approval from the Institutional Review Board (IRB), except where necessary to eliminate an immediate hazard(s) to the trial participants.

| | | |
|---------------------------------------------------------------------------------|-----------------------------------------------------------------|-----------------------|
|  | Treatment with the Evoke System for Facial and Submental Laxity | |
| | Protocol No: DO609886A SIRB ID: | Rev. Date: 29 Oct. 20 |

TABLE OF CONTENTS

1. PROTOCOL SYNOPSIS..... 3

2. INTRODUCTION & STUDY RATIONALE..... 9

3. DEFINITIONS, ACRONYMS AND ABBREVIATIONS 9

4. DEVICE DESCRIPTION.....10

The human skin aging process is characterized by thinning dermis, atrophy of the extracellular matrix, and reduced collagen synthesis. Overwhelming epidemiologic and laboratory evidence indicates that sun exposure and other sources of UV radiation play a major role in causing the undesirable skin changes of fine and coarse wrinkles, roughness, laxity, mottled pigmentation, actinic lentiginos, actinic keratoses, leathery texture/coarseness, scaling/xerosis, shallowness, and telangiectasia¹.

Although facelift surgical procedure remains an extremely effective and popular method to reduce static rhytids, there has been a dramatic paradigm shift toward non-surgical skin tightening and rejuvenation techniques, as patients seek to achieve skin tightening with no or minimal downtime procedures.

Non-ablative energy treatments for skin laxity and rhytides have grown rapidly in the last 10 years. Mid-infrared lasers were initially studied for potential efficacy in skin tightening, but the results were modest and, additionally, the devices could often not be used on darker skin types due to risk of discoloration and scarring following absorption of energy by the chromophore melanin².

Radiofrequency (RF) devices have been reported to achieve modest clinical efficacy in skin tightening without many of the limitations of other energy devices, and may therefore represent an ideal treatment option for non-invasive skin tightening³⁻⁵.

However, most RF treatments are administered by the operator hence, this treatment is time consuming and causes operator fatigue reducing the most effective outcome of the treatment. Evoke device allowing hands free procedure that eliminates operator dependency factor.

The Evoke device is a non-invasive system based on radiofrequency (RF) energies. The Evoke provides a non-invasive approach to achieve a desired aesthetic effect (skin tightening and wrinkle reduction). The system is designed to enable an automatic, hands-free, full facial treatment that is based on a predefined user protocol. In addition, the system incorporates a skin-temperature control into the protocol, enabling accurate, stable and safer treatment.

This prospective study is intended to evaluate the efficacy and safety of Evoke system using radio frequency for wrinkles reduction and skin tightening. Aging is associated with a decrease in collagen turnover due to a decrease in fibroblasts and elastin. The degradation and disorganization of elastin fibers contribute to skin laxity and wrinkles. We may be able to see improvement in histology.

3. Definitions, Acronyms and Abbreviations

| | |
|---------|--------------------------------------|
| RF - | Radiofrequency |
| AE - | Adverse Events |
| SAEs - | Serious Adverse Events |
| UADEs - | Unanticipated Adverse Device Effects |

| | | |
|--------------------------------------------------------------------------------------------------------|------------------------------------------------------------------------|-----------------------|
|  I N M O D E | Treatment with the Evoke System for Facial and Submental Laxity | |
| | Protocol No: DO609886A SIRB ID: | Rev. Date: 29 Oct. 20 |

4. Device Description

The Evoke Platform employs Radio-frequency (RF) technology for various aesthetic applications.

The Evoke System with the Cheek and Chin Applicators is a hands-free medical aesthetic device using RF energy for the treatment of selected medical conditions such as relief of minor muscle aches and pain, relief of muscle spasm, temporary improvement of local blood circulation.

RF energy does not cause any thermal damage to the treated skin. The System provides individual adjustment of RF power to achieve maximum efficiency, safety and comfort for each patient. The System provides enhanced safety while minimizing possible side effects by constantly monitoring RF parameters.

The System incorporates the following safety features. All personnel operating the System should be familiar with these features.

- System has unique password to avoid device operation by non-authorized personnel.
- An audible tone indicates energy activation.
- Special audible tone will be activated in case of bad coupling of one of the applicators.
- During activation, the system performs a self-test of the hardware.
- Hardware is tested every 1 msec. to ensure proper operation of electrical circuits.
- Skin surface temperature is monitored during the treatment. RF energy delivery is terminated when skin temperature accidentally reaches the Cut-Off level.
- System starts at a low setting.

5. Study Objectives

The aim of the study is to evaluate the efficacy, patient comfort and patient satisfaction after Evoke treatment.

Primary Objective:

1. Evaluate improvement in skin appearance comparing pre and at 1 month (except site #3), 3 months and 6 months post last treatment photographs (as assessed by blinded investigators)
2. Evaluate Improvement in skin appearance using 3D Photographic analysis at 1 month (except site #3), 3 months and 6 months follow up visits and compared to the baseline.

Secondary Objective:

1. Evaluate Investigator assessment of the skin appearance improvement comparing pre and post treatment using 0 - 4 -points Likert scale at 1 month (except site #3), 3 months and 6 months follow up visits.

| | | |
|--------------------------------------------------------------------------------------------------------|------------------------------------------------------------------------|-----------------------|
|  I N M O D E | Treatment with the Evoke System for Facial and Submental Laxity | |
| | Protocol No: DO609886A SIRB ID: | Rev. Date: 29 Oct. 20 |

2. Evaluate Subject assessment of improvement and satisfaction using 0 - 4 -points Likert scale at 1 month (except site #3), 3 months and 6 months follow up visits.
3. Optional: Evaluate histological changes to treatment area skin taken at 3M FU versus baseline. (except site #3)

6. Study Endpoints

6.1 Efficacy Endpoints

1. Improvement in in skin laxity comparing pre and at 1 month (except site #3), 3 months and 6 months post last treatment photographs (as assessed by blinded investigators):
 - Success is defined by correct identification of the pre and post treatment photos of patients completed the treatment at 1 month (except site #3), 3 months and 6 months post treatment.
 - At least 2 out of 3 blinded evaluators should agree on the assessment.
2. 3D Photographic analysis will be conducted at 1 month (except site #3), 3 months and 6 months follow up visits and compared to the baseline.
3. Investigator assessment of the skin appearance improvement comparing pre and post treatment using 0 - 4 -points Likert scale at 3 months and 6 months follow up visits:
 - 4 = Significantly marked improvement; 3 = Marked improvement; 2 = Moderate improvement; 1 = Slight improvement; 0 = No difference
4. Improvement assessment will be performed independently by the subject himself 4 points Likert scale questionnaire (Global Aesthetic Improvement Scale), as follows:
 - 4 = Significantly marked improvement; 3 = Marked improvement; 2 = Moderate improvement; 1 = Slight improvement; 0 = No difference.
5. Subject assessment of satisfaction will be filled out by subjects using a 5-points Likert scale, as follows:
 - +2 = Very satisfied; +1 = Satisfied; 0 = Indifferent; -1 = Disappointed; -2 = Very disappointed.
6. Optional: Positive changes in histologic evaluation: up to 5 subjects will undergo biopsies of the treated area for histology at baseline and at 3M follow-up visit. Histological sections will be stained using elastin, H&E and other collagen specific stains.

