8.3 Follow up visits (Visits 4, 5 and 6)

Follow up visits will be conducted at 4 weeks (1-month FU) (except site #3), 12 weeks (3M FU) and 24 weeks (6M FU) following last treatment.

The 1 month (except site #3), **3 months and 6 months follow up visits** will include the following assessments:

- Standardized medical photography
- 3D Photography

| | | |
|--------------------------------------------------------------------------------------------------------|------------------------------------------------------------------------|-----------------------|
|  I N M O D E | Treatment with the Evoke System for Facial and Submental Laxity | |
| | Protocol No: DO609886A SIRB ID: | Rev. Date: 29 Oct. 20 |

- Urine Pregnancy Test (only last 6 months FU visit)
- Investigator assessment of the skin appearance improvement comparing pre and post treatment using 4-point Likert scale
- Subject’s Improvement and Satisfaction questionnaires
- Post final treatment biopsy will be performed (up to 5 subjects)
- AE evaluation recording
- Concomitant medication recording

9. Adverse Events Reporting

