9.2 Anticipated Adverse Events in this Clinical Evaluation

Possible Evoke adverse effects include but are not limited by:

- discomfort or pain,
- excessive skin redness (erythema)
- swelling (edema),
- damage to natural skin texture (crust, blister and burn),
- change of pigmentation (hyper- and hypo-pigmentation),
- bruising,
- scarring.

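### Endpoint 1 is headed as improvement, but its success rule needs only correct pre/post identification, so as written a recognised worsening counts as a success

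*Combined protocol and SAP*

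**What the plan says.** Section 5 (and the Synopsis) gives the first primary objective as "Evaluate improvement in skin appearance comparing pre and at 1 month (except site #3"; the sentence goes on to 3 and 6 months and to assessment by blinded investigators. Endpoint 1 carries this objective. The Synopsis heads it "Improvement in skin appearance comparing pre and at 1 month (except site #3" and section 6.1 heads it "Improvement in in skin laxity comparing pre and at 1 month (except site #3", so the two headings also differ in the attribute named.

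Under both headings the operative rule is the same: "Success is defined by correct identification of the pre and post treatment photos", followed by "At least 2 out of 3 blinded evaluators should agree on the assessment". Neither line states a direction or size of change. Endpoint 6 (optional histology), by contrast, does specify that the changes be positive.

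Three other parts of the plan bear on the point:

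- The investigator and subject improvement scales (endpoints 3 and 4) end at "1 = Slight improvement; 0 = No difference" and have no category for worsening.
- Section 9.2 lists possible visible effects of treatment, among them "change of pigmentation (hyper- and hypo-pigmentation"), texture damage, bruising and scarring.
- Section 14.2 plans paired t-tests on scores. It gives no target, test or chance reference for the endpoint 1 success proportion.

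**The concern.** Correct identification shows that a change can be detected. Improvement is a detected change in one direction. The agreement requirement adds consistency between evaluators but no direction. An evaluator who picks out the follow-up photo because of new pigment change or a scar has identified the pair correctly, and the subject is then a success on an endpoint meant to show improvement.

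This matters because endpoint 1 is the only efficacy endpoint described as blinded, and it serves a primary objective. If worsened subjects are recognised as such, they raise the reported success rate instead of lowering it.

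**Working it through.** The plan gives no expected success rate, threshold or rate of visible worsening, so there is no figure to reproduce. The check has three steps.

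**1. Does the rule depend on direction?** Assume a forced choice and three independent evaluators, each correct with probability p. Subject-level success is P(at least 2 of 3) = 3p²(1−p) + p³.

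- Guessing, p = 0.5: 0.375 + 0.125 = 0.500.
- Recognised pair, p = 0.9 (assumed): 0.243 + 0.729 = 0.972.

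Only p enters. A worsened subject recognised at p = 0.9 is a success with probability 0.972, the same as an improved subject recognised at p = 0.9.

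**2. How far can this move the success rate?** Let I be the share improved and W the share worsened. Let r and r_W be the subject-level (2 of 3) probabilities that improved and worsened pairs are correctly identified. Unchanged pairs are guessed at 0.5. Under a directional rule, a worsened pair succeeds only when the majority misjudges it, with probability 1 − r.

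- Stated rule: I·r + W·r_W + 0.5(1 − I − W)
- Directional rule: I·r + W(1 − r) + 0.5(1 − I − W)
- Difference: W(r_W + r − 1)

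The difference is 0 when r_W = 1 − r, which is what happens if evaluators already call the better photo the later one. Its maximum is W, at r = r_W = 1.

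| W (assumed) | r (assumed) | r_W (assumed) | Difference |
|---|---|---|---|
| 0 | any | any | 0 |
| 0.05 | 1 | 1 | 0.05 × 1 = 5 points |
| 0.10 | 1 | 1 | 0.10 × 1 = 10 points |
| 0.10 | 0.75 | 0.75 | 0.10 × 0.50 = 5 points |
| 0.10 | 0.75 | 0.25 | 0.10 × 0 = 0 |

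Take a device with no net benefit: 10% better, 10% worse, 80% unchanged, all assumed.

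- At r = r_W = 1, the stated rule gives 0.10 + 0.10 + 0.40 = 60% and the directional rule 0.10 + 0 + 0.40 = 50%.
- At r = 0.75 and r_W = 0.25, the stated rule gives 0.075 + 0.025 + 0.40 = 50%, the same as the directional rule.

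The result therefore turns on r_W, that is, on what the evaluators are asked, which the plan does not state.

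**3. What is one subject worth?** Five sites at about 15 give about 75 subjects, so one recognised worsening adds 1/75 = 1.3 points. At 1 month, without site #3, it adds 1/60 = 1.7 points.

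**The case against.** The strongest reply is that the success line should not be read apart from its heading. The heading speaks of improvement, the next line asks evaluators to agree on the assessment, and naming the later photo may simply be how a judgement of improvement is scored. On that reading r_W = 1 − r and the excess is zero. The reading is reasonable, but the available text never gives evaluators that instruction, and the line that defines success does not contain it.

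The instruction might also sit elsewhere. Appendix 1.0 and Appendix 3 are cited but were not in the text available, nor was any evaluator form. By their descriptions in the body, the two appendices are the visit schedule and the discomfort assessment, but an evaluator form could still settle the matter. This limit stands.

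Visible worsening may also be rare. Section 9.2 lists possible effects without rates or durations. Section 8.3 says "Follow up visits will be conducted at 4 weeks (1-month FU) (except site #3"), so the first outcome photo comes 4 weeks after the last treatment and short-lived effects may have cleared. This too stands: W could be close to 0.

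Finally, worsening can show up in adverse event records, in negative satisfaction scores and in the 3D analysis, which is itself a primary objective although its metric is not specified. That is true, but none of these takes a worsened subject out of the endpoint 1 success count.

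**Conclusion.** The point holds as a defect of definition: the stated rule scores detectability, while the heading and objective claim improvement. It should be corrected, because the endpoint is the blinded one and serves a primary objective.

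Its size is not derivable. The excess is W(r_W + r − 1), from 0 when evaluators already treat the better photo as the later one up to W. Every value of W, r and r_W above is an assumption, as are forced choice and guessing at 50% for unchanged pairs.

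A reader might infer more than the documents support:

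- That worsened subjects will be counted, or that the success rate will be inflated by 5 to 10 points. Those figures require evaluators to recognise harm as the mark of the later photo, and the plan does not say how they will judge.
- That the study cannot record worsening at all. It can, outside endpoint 1.
- That a declared success decision would be overturned. No threshold or test is stated for this proportion.
- That optional biopsies would reveal the later photo. The biopsy site and the visibility of any mark are not stated, so this forms no part of the finding.

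**What to change.** Replace the success rule in the Synopsis and in section 6.1 with:

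*Each baseline/follow-up pair is shown in random, unlabelled order. Each of the three blinded evaluators states which photo shows the better skin appearance. Success = at least 2 of 3 choose the post-treatment photo.*

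Report the success rate next to the 50% expected from guessing, since unchanged pairs in a forced choice still succeed about half the time.

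Separately, reconcile skin laxity (endpoint 1 in section 6.1) with skin appearance (Synopsis and section 5). The study title and the population description speak of laxity, so the sponsor should decide which attribute is meant and use the same term in the evaluators' question.

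The cost is one changed question, with the same photos and the same three evaluators. If the sponsor already intended a judgement of improvement, the change only writes that down. The main drawback is that an evaluator who still recognises the later photo may favour it, so the bias is reduced but not removed.
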